10.1.16. On-Site Audits

Representatives of the Sponsor's clinical quality assurance department or designee may visit the study site at any time during or after completion of the study to conduct an audit of the study in compliance with regulatory guidelines and company policy. These audits will require access to all study records, including source documents, for inspection. Participant privacy must, however, be respected. The Investigator and study-site personnel are responsible for being present and available for consultation during routinely scheduled study-site audit visits conducted by the Sponsor or its designees.

Similar auditing procedures may also be conducted by agents of any regulatory body, either as part of a national GCP compliance program or to review the results of this study in support of a regulatory submission. The Investigator should immediately notify the Sponsor if he or she has been contacted by a regulatory agency concerning an upcoming inspection.

10.3.1. Definition of AE

AE Definition

- An AE is any untoward medical occurrence in a patient or clinical study participant, temporally associated with the use of study intervention, whether or not considered related to the study intervention.
- NOTE: An AE can therefore be any unfavorable and unintended sign (including an abnormal laboratory finding), symptom, or disease (new or exacerbated) temporally associated with the use of study intervention.
- Hypoglycemia and hyperglycemia will be reported as adverse events only in the case of requiring the assistance of others due to loss of consciousness or diabetic ketoacidosis (DKA).

Unexpected AE:

- An adverse event is considered unexpected when the nature (specificity) or severity of the event is not consistent with the risks described in the Investigator's Brochure or the informed consent document.

Events Meeting the AE Definition

- Any abnormal laboratory test results (hematology, clinical chemistry, or urinalysis) or other safety assessments (e.g., ECG, radiological scans, vital signs measurements), including those that worsen from baseline, considered clinically significant in the medical and scientific judgment of the investigator (i.e., not related to progression of underlying disease).
- Exacerbation of a chronic or intermittent pre-existing condition including either an increase in frequency and/or intensity of the condition.
- New conditions detected or diagnosed after study intervention administration even though it may have been present before the start of the study.
- Signs, symptoms, or the clinical sequelae of a suspected drug-drug interaction.
- Signs, symptoms, or the clinical sequelae of a suspected overdose of either study intervention or a concomitant medication. Overdose per se will not be reported as an AE/SAE unless it is an intentional overdose taken with possible suicidal/self-harming intent. Such overdoses should be reported regardless of sequelae.

Events NOT Meeting the AE Definition

- Any clinically significant abnormal laboratory findings or other abnormal safety assessments which are associated with the underlying disease, unless judged by the investigator to be more severe than expected for the participant's condition.
- The disease/disorder being studied or expected progression, signs, or symptoms of the disease/disorder being studied, unless more severe than expected for the participant's condition.
- Medical or surgical procedure (e.g., endoscopy, appendectomy): the condition that leads to the procedure is the AE.
- Situations in which an untoward medical occurrence did not occur (social and/or convenience admission to a hospital).
- Anticipated day-to-day fluctuations of pre-existing disease(s) or condition(s) present or detected at the start of the study that do not worsen.

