8.3.1.1. Hypoglycemia

Instances of significant impairment consistent with hypoglycemia and requiring assistance (ie, often referred to as “severe” hypoglycemia), even in the absence of a blood glucose reading, are classified as “Level 3 Hypoglycemia” ([IHSG 2017](#)). Level 3 hypoglycemia may include cognitive impairment, altered/loss of consciousness, confusion, seizure, syncope/fainting, or coma, and support may be general assistance, glucagon, or oral carbohydrate (ie, fruit juice or glucose tablets). Such episodes may or may not require medical attention or hospitalization.

This study will consider clinically significant hypoglycemia to be Level 3 or greater hypoglycemia as defined below.

For AE reporting purpose, the severity of a hypoglycemia event should be identified by the Investigator and classified according to CTCAE v5.0 as follows:

- Grade 3 hypoglycemia: 30-39 mg/dL (1.7–2.1 mmol/L). This is considered severe or medically significant but not immediately life-threatening. Hospitalization or prolongation of hospitalization is likely indicated. It is considered disabling and limits self-care.
- Grade 4 hypoglycemia: ≤ 29 mg/dL (1.6 mmol/L). This is considered life threatening (eg, seizures) with urgent intervention indicated.
- Grade 5 hypoglycemia: Hypoglycemia resulting in death.

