10.3.3. Definition of AESI

The following types of AEs are considered AESIs:

- All infections: viral, fungal, bacterial
- Acute mononucleosis-like illness (eg, fever, pharyngitis, lymphadenopathy)
- CMV viremia defined using DNA PCR testing and >10,000 copies per mL serum or 10⁶ cells
- EBV viremia defined using DNA PCR testing and >10,000 copies per mL serum or 10⁶ cells
- Herpes zoster or other conditions related to VZV
- Primary infection with or reactivation of latent tuberculosis
- Infections requiring IV antibiotic treatment
- Demyelinating diseases
- Malignancies including lymphomas
- Severe hypoglycemic episodes that require assistance by another individual through the administration of oral or parenteral dextrose, glucagon or intervention
- ≥ Grade 3 liver function abnormalities (AST, ALT, bilirubin)
- ≥ Grade 3 thrombocytopenia (platelet counts less than 50,000/µL)
- ≥ Grade 3 allergic/hypersensitivity reaction (anaphylaxis)
- ≥ Grade 3 Rash

- \geq Grade 3 cytokine-release syndrome
- \geq Grade 4 neutropenia (<500 PMN/ μ L on 2 consecutive evaluations performed on different days)

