These events will be captured on the CRF and reported to the Sponsor as described in Section 8.4.1.1. Any event that meets serious adverse event criteria will be reported to the Sponsor within the appropriate timeline as described in Section 8.4.1.4.

Events will be assessed and reported consistent with the ICH Guideline for Good Clinical Practice and per the guidance of the DHHS Office for Human Research Protections (OHRP).

Event outcome and other follow-up information regarding the treatment and resolution of the event will be obtained and reported when available, if not known at the time the event is initially reported. The follow-up information should contain sufficient detail to allow for a complete medical assessment of the case and an independent determination of possible causality.

AESIs should be reported according to the requirements for SAEs.

Assessment of Severity

An assessment of severity grade for each AE will be made by the site Investigator according to the criteria set forth in the National Cancer Institute's Common Terminology Criteria for Adverse Events Version 5.0. This document (referred to herein as the "CTCAE V5.0") provides a common language to describe levels of severity, to analyze and interpret data, and to articulate the clinical significance of all AEs. The Investigator should use clinical judgment in assessing the severity of events not directly experienced by the participant (eg, laboratory abnormalities).

Adverse events will be graded according to National Cancer Institute (NCI) Common Terminology Criteria for Adverse Events (CTCAE) version 5.0:

- Grade 1 = Mild adverse event.
- Grade 2 = Moderate adverse event.
- Grade 3 = Severe adverse event.
- Grade 4 = Life-threatening or disabling adverse event.
- Grade 5 = Death

Assessment of Causality

The Investigator is required to provide an assessment of causality or relationship of adverse events to the study drug based on 1) temporal relationship of the event to the administration of study drug; 2) whether an alternative etiology has been identified; and 3) biological plausibility. The causality assessment categories that will be used for this study are described below.

Causality assessments considered **not** related to study drug:

- Unrelated: The event is related to an etiology other than the study drug (the alternative etiology must be documented in the participant's medical record).

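### Protocol 10.3.1 and 10.3.3 conflict on which assisted hypoglycaemic episodes are reported, and SAP 7.8.5 lists the hypoglycaemia endpoint by a search with no assistance criterion

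*Protocol*

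**What the plan says.** **Reporting.** Protocol 10.3.1 (Definition of AE) says that "Hypoglycemia and hyperglycemia will be reported as adverse events only in the case of requiring the assistance of others due to loss of consciousness"; the sentence then adds diabetic ketoacidosis. Protocol 10.3.3 (Definition of AESI) introduces its list as types of adverse event and includes "Severe hypoglycemic episodes that require assistance by another individual", through dextrose, glucagon or another intervention. Protocol 10.3.4 adds that "AESIs should be reported according to the requirements for SAEs". Protocol 10.3.2 says that an event outside the AE definition cannot be an SAE, even when a seriousness criterion is met.

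**Clinical definition.** Protocol 8.3.1.1 describes Level 3 hypoglycaemia as impairment for which help is needed, "even in the absence of a blood glucose reading". Confusion or cognitive impairment is enough, and "support may be general assistance, glucagon, or oral carbohydrate". It continues: "This study will consider clinically significant hypoglycemia to be Level 3 or greater hypoglycemia as defined below". What stands below that sentence, however, is a set of CTCAE grades, beginning with "Grade 3 hypoglycemia: 30-39 mg/dL".

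**Endpoint and analysis.** Protocol section 3 and SAP section 2 make the frequency of clinically important hypoglycaemia over 78 weeks part of a secondary endpoint, together with HbA1c and insulin use. Protocol 9.4.2 promises a descriptive treatment of HbA1c and insulin use and does not mention hypoglycaemia. SAP 7.8.5 provides a data listing of severe episodes based on the AESI search in SAP Table 2: three preferred terms (hypoglycaemic seizure, coma, unconsciousness) at any grade, or the preferred term Hypoglycaemia at Grade 3 or above. SAP 7.10 declares that the AESI definition differs from the protocol's and follows one agreed with FDA for the integrated safety summary. It does not mention the hypoglycaemia endpoint.

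**The concern.** Take a participant who is confused but conscious and is given glucagon by a parent. Under 10.3.3 and 10.3.4 this is an AESI, to be reported as an SAE would be. Under 10.3.1 it is not an adverse event at all. Two sites could each follow the protocol and record different things.

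The primary endpoint is the incidence of TEAEs, AESIs and SAEs, so the conflict reaches it directly. It also reaches the secondary hypoglycaemia endpoint, because SAP 7.8.5 draws on reported adverse events. A low or zero count could then partly reflect which rule a site applied.

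The second issue is independent of the first. Even for episodes that are reported, the endpoint threshold in 8.3.1.1 can be read in two ways, and the SAP search fits one reading better than the other.

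**Working it through.** No sample size, rate or test bears on this point, so the check is a comparison of rules.

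**Step 1: can 10.3.1 and 10.3.3 both be followed?** Section 10.3.3 treats AESIs as a subset of adverse events. An episode excluded by 10.3.1 therefore cannot be an AESI without contradiction, and by 10.3.2 it cannot be an SAE either, even if the participant was admitted to hospital. Section 10.3.1 is itself specific to hypoglycaemia and hyperglycaemia and is worded as exclusive, so it is not a general rule that simply yields to a more specific one. No text gives either section precedence.

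**Step 2: apply each rule to example episodes.** Helped means that another person gave glucose or glucagon. Grades use the 8.3.1.1 glucose bands (30–39 mg/dL is Grade 3; 29 mg/dL or less is Grade 4). The last column assumes that the episode was reported.

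| Episode | AE under 10.3.1 | Level 3 text in 8.3.1.1 | AESI under 10.3.3 | Grade 3+ by glucose band | Found by SAP Table 2 |
|---|---|---|---|---|---|
| Helped, lost consciousness, coded to unconsciousness | yes | yes | yes | depends on reading | yes |
| Helped, conscious, 35 mg/dL | no | yes | yes | yes | yes |
| Helped, conscious, 45 mg/dL | no | yes | yes | no | no, if graded by band alone |
| Helped, conscious, no reading | no | yes | yes | cannot be placed | depends on investigator's grade |
| Not helped, 35 mg/dL | no | no | no | yes | yes |

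The three rows for helped, conscious participants show the reporting conflict. The 45 mg/dL and unhelped rows show how the search can depart from an assistance-based endpoint in each direction. These examples show that the rules diverge; they are not frequencies.

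**Step 3: which threshold does 8.3.1.1 set?** The closing pointer of the sentence on clinically significant hypoglycaemia leads to Grades 3 to 5, while Level 3 is described above it, and no level beyond 3 is defined. If the threshold is assistance, the Level 3 column applies. If it is grade, the Grade 3+ column applies, and the SAP search largely agrees with it. The text does not settle the choice.

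**Step 4: is there another route of capture?** The Schedule of Events has an adverse event review row and no hypoglycaemia row. Protocol 8.3.1 has insulin use and HbA1c documented. On the other side, 8.3 includes monitoring of diabetes control, 10.1.10 requires source records for protocol-required efficacy parameters as well as adverse events, and the CRF is not among the documents. A separate field can be neither confirmed nor excluded.

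**The case against.** **Sites would follow the AESI rule.** Section 10.3.3 names assisted episodes, 10.3.4 tells sites to report AESIs, and the list of exceptions in 7.2 presupposes graded hypoglycaemia events. A reader might infer that helped, conscious episodes will go unreported and appear nowhere. The documents do not support that: sites may well apply 10.3.3, and source records or a CRF field may hold the episodes. What stands is that reporting may vary, because 10.3.1 says the opposite.

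**The SAP may match the protocol.** A reader might infer that SAP 7.8.5 plainly contradicts the protocol's endpoint. That goes too far. On the grade reading of 8.3.1.1, the unhelped 35 mg/dL episode belongs and the 45 mg/dL one does not. The latter is also not a certain miss on the assistance reading: the investigator assigns severity, and the Grade 3 text includes "It is considered disabling and limits self-care", which could describe a helped episode at any glucose value. The unhelped episode is reportable under neither 10.3.1 nor 10.3.3, so it enters only if a site reports it anyway. For these reasons a hit-and-miss tally from the examples would carry no weight.

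**The AESI change is declared, and listings are deliberate.** Both are true. SAP 7.10 discloses the change, and the SAP's document history explains the move to listings by expected enrolment, with a maximum of 30 participants. A summary table is therefore a preference. The disclosure still does not say that a secondary endpoint is carried along with the AESI definition. Nor does 7.8.5 call itself the analysis of that endpoint; this is inferred from its being the only hypoglycaemia section among the SAP's analyses of the secondary endpoints.

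**Conclusion.** The protocol is wrong as written on reporting: 10.3.1 excludes helped, conscious episodes that 10.3.3 and 10.3.4 require to be reported. This should be fixed, because it bears on the primary safety counts as well as a secondary endpoint. Confidence is high for this part, which rests on the text alone.

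The SAP part is conditional. The endpoint threshold is ambiguous between assistance and grade. If it is assistance, the SAP 7.8.5 search can omit a helped episode coded Hypoglycaemia and graded below 3, and can include an unhelped Grade 3 episode if one is reported. If it is grade, the mismatch largely disappears.

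The size cannot be stated, since the documents give no rate of hypoglycaemia. Episodes that are reported but missed by the search remain in the TEAE tables and listing. Only episodes not reported as adverse events could be lost to the analysis, and then only if no other record captures them. All analyses are descriptive, so no test or error rate is affected.

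**What to change.** 1. Reconcile Protocol 10.3.1, 8.3.1.1 and 10.3.3 so that a single reporting rule applies to hypoglycaemia.
2. In 8.3.1.1, state whether clinically significant hypoglycaemia refers to the Level 3 description above the sentence or to the CTCAE grades below it.
3. Leave the FDA-aligned AESI search in SAP Table 2 as it is. In SAP 7.8.5, give the endpoint its own definition, matching the reconciled protocol text, and declare any difference from the AESI search in SAP 7.10.
4. If follow-up is already complete, which the documents do not say, a protocol edit comes too late to change reporting. Query sites for assisted episodes in source records, and state any remaining under-capture as a limitation.

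A count by prior TN-10 treatment next to the listing is optional. HbA1c and insulin use, from the same endpoint row, are already presented that way in SAP 7.8.2 and 7.8.3.

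The cost is a few protocol sentences, a sentence each in SAP 7.8.5 and 7.10, some site queries with incomplete recovery of older episodes, and a footnote where the endpoint and AESI listings differ. An assistance flag is needed only if assistance becomes the criterion and the CRF does not already record it.

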10.3.2. Definition of SAE

If an event is not an AE per definition above, then it cannot be an SAE even if serious conditions are met (e.g., hospitalization for signs/symptoms of the disease under study, death due to progression of disease).

An SAE is defined as any untoward medical occurrence that, at any dose:**a. Results in death****b. Is life-threatening**

The term 'life-threatening' in the definition of 'serious' refers to an event in which the participant was at risk of death at the time of the event. It does not refer to an event, which hypothetically might have caused death, if it were more severe.

c. Requires inpatient hospitalization or prolongation of existing hospitalization

- In general, hospitalization signifies that the participant has been detained (usually involving at least an overnight stay) at the hospital or emergency ward for observation and/or treatment that would not have been appropriate in the physician's office or outpatient setting. Complications that occur during hospitalization are AEs. If a complication prolongs hospitalization or fulfills any other serious criteria, the event is serious. When in doubt as to whether "hospitalization" occurred or was necessary, the AE should be considered serious.
- Hospitalization for elective treatment of a pre-existing condition that did not worsen from baseline is not considered an AE.

d. Results in persistent disability/incapacity

- The term disability means a substantial disruption of a person's ability to conduct normal life functions.
- This definition is not intended to include experiences of relatively minor medical significance such as uncomplicated headache, nausea, vomiting, diarrhea, influenza, and accidental trauma (e.g., sprained ankle) which may interfere with or prevent everyday life functions but do not constitute a substantial disruption.

e. Is a congenital anomaly/birth defect**f. Other situations:**

- Medical or scientific judgment should be exercised in deciding whether SAE reporting is appropriate in other situations such as important medical events that may not be immediately life-threatening or result in death or hospitalization but may jeopardize the participant or may require medical or surgical intervention to prevent one of the other outcomes listed in the above definition. These events should usually be considered serious.
- Examples of such events include invasive or malignant cancers, intensive treatment in an emergency room or at home for allergic bronchospasm, blood dyscrasias or convulsions that do not result in hospitalization, or development of drug dependency or drug abuse.

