10.3.4. Reporting and Follow-Up of AE and/or SAE

AE and SAE Reporting

Timely, accurate, and complete reporting and analysis of safety information from clinical studies are crucial for the protection of participants, Investigators, and the Sponsor, and are mandated by regulatory agencies worldwide. The Sponsor has established Standard Operating Procedures in conformity with regulatory requirements worldwide to ensure appropriate reporting of safety information; all clinical studies conducted by the Sponsor or its affiliates will be conducted in accordance with those procedures.

The determination of seriousness, severity and causality must be made by the physician Investigator who is qualified to review adverse event information, provide a medical evaluation of adverse events, and classify adverse events based upon medical judgment.

An adverse event is any untoward medical occurrence in a clinical study participant from the time they formally agree to participate in the study (eg, by providing informed consent/assent) through their last study contact (eg, last visit or status update). An adverse event does not necessarily have a causal relationship with the study drug. An adverse event can therefore be any unfavorable and unintended sign (including an abnormal finding), symptom, or disease temporally associated with the use of a study drug (investigational or non-investigational product), whether or not related to that study drug (investigational or non-investigational product).

This includes any occurrence that is new in onset or aggravated in severity or frequency from the baseline condition, or abnormal results of diagnostic procedures, including laboratory test abnormalities.

A treatment-emergent adverse event (TEAE) is defined as an AE that occurs after the first dose of study drug administration (Day 1) through the end of the study or early termination.

The Investigator must follow all SAEs (including serious AESIs) until resolution even if this extends beyond the study-reporting period. Resolution of a SAE is defined as the return to pre-treatment status or stabilization of the condition with the expectation that it will remain chronic. At any time after completion of the study, if an Investigator becomes aware of a serious adverse event that s/he suspects is related to study drug, the Investigator should report the event to the Pharmacovigilance contact.

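### The protocol's AE definition sets a narrower threshold for glycemic events than its other sections, and the SAE rule inherits it, so some diabetes-attributed events can be missing from the primary safety counts

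*Protocol*

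**What the plan says.** The primary endpoint is the incidence of TEAEs, AESIs and SAEs (Protocol 3; SAP 2) in a single-arm, open-label trial.

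- **Protocol 10.3.2** puts a condition ahead of the seriousness criteria: "If an event is not an AE per definition above, then it cannot be an SAE even if serious conditions are met". Its examples are "hospitalization for signs/symptoms of the disease under study, death due to progression of disease".
- **Protocol 10.3.1** supplies the AE definition on which that condition depends. Hypoglycemia and hyperglycemia are reported as AEs "only in the case of requiring the assistance of others due to loss of consciousness or diabetic ketoacidosis (DKA"). Its list of events that are not AEs includes "expected progression, signs, or symptoms of the disease/disorder being studied, unless more severe than expected for the participant's condition".
- **Protocol 10.3.3** lists this among the types of AE that count as AESIs: "Severe hypoglycemic episodes that require assistance by another individual through the administration of oral or parenteral dextrose, glucagon or intervention". Under 10.3.4, AESIs follow the SAE reporting requirements.
- **Protocol 8.3.1.1** defines Level 3 hypoglycemia by impairment needing assistance, which may be confusion alone. It also grades hypoglycemia by glucose value for AE reporting, ending with "Grade 5 hypoglycemia: Hypoglycemia resulting in death".
- **Protocol 7.2** names hypoglycemia and hyperglycemia among the AEs of Grade 3 or higher that are exempt from its discontinuation rule, so it treats them as AEs with a grade.
- **SAP 7.7.1 and 7.8.5** build the TEAE, serious TEAE, AESI and severe-hypoglycemia outputs from adverse event terms and grades. SAP 7.10 lists the departures from the protocol and leaves the SAE definition alone.

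**The concern.** An event enters the primary endpoint only if a site first records it as an AE. For glycemic events, the protocol gives sites different thresholds for doing so. For other diabetes signs and symptoms, it leaves the decision to an investigator who knows the treatment and has no criterion for what counts as worse than expected. Two sites could handle the same episode differently and both be following the protocol.

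The design makes this harder to detect, because no concurrent arm would show an excess of admissions put down to diabetes. The distinction also bears on drug safety. The protocol permits short corticosteroid courses (6.3.3) and insulin reduction or discontinuation (6.3.1), and either could precede an admission labelled as diabetes.

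**Working it through.** The plan has no figure to reproduce: there is no sample-size calculation, expected SAE rate or hypothesis test. The check is a comparison of the definitions, followed by simple arithmetic on what one missed participant would do.

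**Step 1. Run typical events through the definitions.**

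| Event | AE under 10.3.1? | Other protocol sections | Can it be an SAE under 10.3.2 if serious? |
|---|---|---|---|
| Hypoglycemia with confusion, helped by another person, no loss of consciousness | No, on the glycemic rule | Level 3 in 8.3.1.1; an AESI, hence an AE, in 10.3.3 | Contradictory |
| Admission for hyperglycemia without ketoacidosis or loss of consciousness | No on the glycemic rule; at best only if judged worse than expected | Gradable AE in 7.2; no AESI category | No, or by judgement |
| Admission for another sign or symptom of diabetes | Only if judged worse than expected | None specific | By judgement |
| Ketoacidosis | Yes | None needed | Yes |
| Glycemic event with loss of consciousness needing help | Yes | Hypoglycemia is also Level 3 and an AESI | Yes |

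The first two rows are the firm part of the gap. The glycemic rule in 10.3.1 contains the word only and has no severity exception of its own. The exception for unexpectedly severe events stands in a separate list, and the protocol does not say which rule prevails.

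**Step 2. Trace an unrecorded event through the SAP.** The overall TEAE summary, the serious TEAE tables and the AESI table (7.7.1) all start from adverse event records. The AESI search for severe hypoglycemia uses preferred terms and grade, and the listing in 7.8.5 uses the same search. That listing is the SAP's only dedicated output for the hypoglycemia secondary endpoint. An event never entered as an AE reaches none of these. Death is tabulated separately as a reason for leaving the study (7.3). No output is specified for hospitalizations as such.

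**Step 3. Size of one omission.** If a participant's only SAE is not recorded, observed SAE incidence falls by 1/n. The protocol gives a maximum n of 30 (4.1) or 33 (9.2). SAP 7.10 says enrolment was small but gives no number, so n = 10 is an assumption. Exact (Clopper-Pearson) 95% intervals are added for illustration; the SAP plans none. With no events, the upper limit is 1 − 0.025^(1/n).

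| n | No SAE counted | One SAE counted | Shift |
|---|---|---|---|
| 33 | 0% (0 to 10.6) | 3.0% (0.1 to 15.8) | 1/33 = 3.0 points |
| 30 | 0% (0 to 11.6) | 3.3% (0.1 to 17.2) | 1/30 = 3.3 points |
| 10 (assumed) | 0% (0 to 30.8) | 10% (0.3 to 44.5) | 1/10 = 10 points |

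The same 1/n applies to AESI incidence. The row for any TEAE is less sensitive, because a participant with an omitted event may well have another TEAE.

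**The case against.** A reader might infer from the examples in 10.3.2 that no hospitalization or death attributed to diabetes can be an SAE, and that the gravest outcomes therefore leave the endpoint. The documents do not support that. The bar is conditional on failing the AE definition. Section 10.3.1 keeps ketoacidosis, glycemic events with loss of consciousness needing help, and anything judged worse than expected, which together cover the main acute life-threatening diabetes events the protocol names.

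Other parts of a stronger case also fail:

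- The ketoacidosis death in the earlier Phase 2/3 trial (Protocol 2.3) would be an AE and a fatal SAE here, so it illustrates capture, not loss.
- A fatal hypoglycemia would ordinarily involve loss of consciousness and so stay reportable. The Grade 5 category is weak evidence of a conflict.
- Section 10.3.4 says "An adverse event is any untoward medical occurrence in a clinical study participant from the time they formally agree to participate in the study" without a disease exclusion. However, 10.3.1 opens in equally general terms before listing its exclusions, so this can be read as general text followed by specific text.
- Infection after dosing is itself an AE, and under 10.3.3 an AESI reported like an SAE. A drug reaction needing steroids is also an AE in its own right.
- Deaths appear in the SAP's disposition table whatever their attribution.
- The 1/n arithmetic applies to any miscounted event and gives no rate of omission. The analysis is descriptive, so no formal inference is distorted.

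All of this stands, and it narrows the point. It does not resolve the conflict over assisted hypoglycemia, recover a hyperglycemia admission without ketoacidosis or loss of consciousness, or supply a criterion for the severity judgement.

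**Conclusion.** The concern holds in a limited form. Sections 8.3.1.1, 10.3.1 and 10.3.3 set incompatible thresholds for when hypoglycemia is reportable, and 10.3.1 does not fit the treatment of both glycemic disturbances in 7.2. The rule in 10.3.2 carries the narrowest threshold into SAE status. Followed literally, some diabetes-attributed episodes and admissions can be missing from the primary endpoint and from the SAP's AE outputs. Each participant so omitted costs about 3 percentage points of SAE or AESI incidence at the planned maximum, and 10 points at an assumed n of 10.

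This rests on three assumptions. Sites apply the glycemic rule in 10.3.1 as written. Ketoacidosis is reportable in its own right; the grammar of that rule would also allow a narrower reading. The omitted participant has no other counted event of the same class. The documents do not show how often an omission would occur. The point merits correction because it decides what the primary endpoint counts and the correction is cheap.

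**What to change.** 1. **Protocol 8.3.1.1, 10.3.1, 10.3.2, 10.3.3 and 10.3.4:** reconcile these to one reporting definition for hypoglycemia and hyperglycemia, and state which rule prevails over the general disease exclusion. Check that the AE terms used in 7.2 agree with it. This concerns recording only and leaves the discontinuation rule as it is.
2. **Protocol 10.3.2:** remove the disease-under-study examples, and state that all deaths and all unplanned hospitalizations after consent are recorded whatever the cause, with attribution to type 1 diabetes captured in a separate field.
3. **SAP 7.7.1:** add a line for all-cause death and hospitalization to the overall safety summary, with a supporting listing. For participants whose follow-up has ended, ask sites about admissions attributed to diabetes and list them.

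The cost is a short amendment or reporting clarification, a few more forms, one table line and one listing. Reported SAE incidence may rise slightly, and the separate attribution field lets a reader see why.
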